2.3 Exploratory Objectives & Endpoints

- NY-ESO-1 and MAGE antigens' promoter methylation (pyrosequencing) and mRNA expression levels (quantitative RT-PCR) will be measured before and after treatment in DNA (plasma and/or tumor biopsies) and RNA (tumor biopsies), respectively.
- Cytokine response (IFN γ IL2, IL6, IL10, TNF α) will be measured in plasma by ELISA.
- Measure LINE 1 methylation in DNA extracted from PBMCs (measured on days 1 and 5 of cycles 1 and 2).
- Expression of the PD-L1 ligand will be measured by IHC in archival tumors.
- Tumor infiltrating lymphocytes (TILs) will be quantified in tumor biopsies before and after treatment (IHC), including in optional samples collected > 6 months on treatment.

3.0 PATIENT ELIGIBILITY

The target population for this study is patients with platinum resistant recurrent ovarian cancer. This will be a multicenter-trial conducted at Robert H. Lurie Comprehensive Cancer Center of Northwestern University (RHLC). Northwestern University will serve as the lead site and coordinating center for this study. Participating sites will include the University of Chicago.

A total of up to 46 subjects will be needed to obtain 35 evaluable subjects for this trial. Approximately 6-8 potentially eligible patients are seen per month, and it is anticipated that at least 1-2 per month will be accrued.

Subjects must meet all of the inclusion and none of the exclusion criteria to be registered to the study. Study treatment may not begin until a subject is registered. Please refer to Section 11 for complete instructions regarding registration procedures.

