Short Title	Guadecitabine and pembrolizumab in platinum resistant recurrent ovarian cancer
Version	November 18, 2020 (Amendment 11)
Study Design	This will be an open label phase II trial with a safety run-in component testing the experimental combination of guadecitabine and pembrolizumab.
Study Center(s)	Lead site: Robert H. Lurie Comprehensive Cancer Center (RHLCCC) Affiliate site: University of Chicago
Objectives	
Primary Objective:
 
Measure Objective Response Rate (ORR) to guadecitabine and pembrolizumab in patients with recurrent platinum resistant ovarian cancer.
 
Secondary Objectives:
 
 • Measure Progression Free Survival (PFS) and Clinical Benefit Rate (CBR) to the combination of guadecitabine and pembrolizumab. • Measure toxicity profiles to the combination of guadecitabine and pembrolizumab. 
Refer to Section 2.0 for Exploratory Objectives.

Sample Size	Maximum accrual limit: 46 Evaluable subjects: 35
ESTIMATED ENROLLMENT PERIOD	Estimated 24 months
ESTIMATED STUDY DURATION	Estimated 36 months

NU Study Number: NU 16G03
Merck Study Number: 3475-244

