Statistical Methodology	
This is a non-randomized, open label phase II study. Study endpoints are defined in Section 6.0
 
We will utilize the optimum two stage design, and we anticipate enrolling 35 evaluable patients. This two-stage design, which will test the null hypothesis that ORR<=0.10 versus the alternative that ORR>=0.30 (where ORR is calculated via RECIST v1.1), has an expected sample size of 22.5 and a probability of early termination of 0.71 when ORR=0.10. If the drug combination is actually not effective, there is a 0.047 probability of concluding that it is (the target for this value was 0.050). If the drug is actually effective, there is a 0.098 probability of concluding that it is not (the target for this value was 0.100). After testing the drug on 18 patients in the first stage, consideration will be given to trial termination if 2 or fewer patients demonstrate clinical benefit (CR, PR, or SD for at least 3 months). If the trial goes on to the second stage, a total of 35 evaluable patients will be studied. If the total number responding is less than or equal to 6, the combination is rejected. Subjects who are not evaluable for response will be replaced so that up to 46 subjects will be enrolled.

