4.11 Patient Replacement

If a patient is enrolled in the study but comes off study prior to the first dose of treatment, the patient may be replaced.

If a subject in the safety run-in portion of the trial goes off treatment before completing the DLT observation period of safety run-in for reasons other than DLT, then a patient will need to be added to the safety run-in.

5.0 STUDY PROCEDURES AND SCHEDULE OF EVENTS**5.1 COMBINATION TREATMENT GUADECITABINE + PEMBROLIZUMAB**

Time Period	Screening		On Treatment ¹⁵			Off Treatment	
	≤28 days prior to registration	≤14 days prior to registration	Cycle 1 ¹⁴	Cycle 2	Subsequent cycles	≥ 6 months of treatment ¹⁷	30 days post last dose ¹²
Required Assessments							
Informed Consent	X						
Medical history ¹	X						
Physical exam ²		X	D1 ²	D1 ²	D1 ²		X
CBC ³		X	D1 ³	D1 ³	D		X
CMP ³		X	D1 ³	D1 ³	D		X
CA 125 ³	X		D1 ³	D1 ³	D		X
Mg, Phos, LDH		X					
PT/INR & aPTT		X					
Thyroid Function and Uric acid ¹¹		X			D1 ¹¹		
Pregnancy test	X ⁸		D1 ⁸	D1 ⁸	D1 ⁸		
Adverse events ¹⁶		X	D1	D1	D1		X
Con Meds ¹⁶		X	D1	D1	D1		X
CXR or CT of chest ⁴	X				X		X ¹³
CT or MRI of abdomen & pelvis ⁴	X				X		X ¹³
Pembrolizumab ¹⁵			D5	D5	D5		
Guadecitabine ¹⁵			D1-4	D1-4	D1-4		
Archival tumor tissue ⁵			X				
Blood for DNA analysis ⁶			C1D1	C2D8		X ¹⁷	
Blood for cytokine response ⁷			C1D1	C2D1	C3D1	X ¹⁷	X
Blood for PBMC analysis ⁹			X	X		X ¹⁷	X
Tumor biopsy ¹⁰			X	X		X ¹⁷	
Survival status							X
Subsequent therapy							X

1. Includes diagnosis and staging [pathology report and Tumor Node Metastasis (TNM) staging should be collected].

2. Physical exam includes vital signs [blood pressure, weight, height (screening only)] and ECOG performance status. Physical exam will be conducted on Day 1 (+/-4 days) of each cycle and at the safety follow-up visit, which occurs 30 days post last dose.

3. Labs to be done within ≤4 days of D1. Cycle 1 Day 1 CBC and CMP do not need to be repeated if screening labs

NU Study Number: NU 16G03

Merck Study Number: 3475-244

were done ≤ 4 days prior to starting treatment. CA-125 is to be drawn at screening and Day 1 of each cycle. Exceptions would be if CA-125 was drawn within 14 days from the screening visit or within 14 days of visits where doses have been delayed. In these cases, CA-125 will not need to be re-drawn. CBC = Complete Blood Cell Count with diff. CMP = Na, K, Cl, creatinine, BUN; liver function tests (LFTs) to include AST, ALT, total bilirubin, alkaline phosphatase.

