6.2 Primary Endpoint

Measure **Objective Response Rate (ORR)** to guadecitabine and pembrolizumab in patients with recurrent platinum resistant Ovarian Cancer. Any patient who has completed at **least 2 cycles** of treatment will be evaluable for this endpoint.

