10.2 Sample Size and Accrual

We will utilize the optimum two-stage design and we anticipate enrolling 35 evaluable patients. This two-stage design to test the null hypothesis that $RR \leq 0.10$ versus the alternative that $RR \geq 0.30$ (where RR is calculated via RECIST v1.1) has an expected sample size of 22.5 and a probability of early termination of 0.71 when $RR = 0.10$. If the drug combination is actually not effective, there is a 0.047 probability of concluding that it is (the target for this value was 0.050). If the drug is actually effective, there is a 0.098 probability of concluding that it is not (the target for this value was 0.100). Subjects who are not evaluable for response will be replaced so up to 46 subjects may be enrolled.

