10.4.2 Efficacy Criteria

As this is a two-stage design, an interim efficacy analysis is planned after 18 patients are evaluable (see 10.2 for additional details). After testing the drug on 18 patients in the first stage, consideration will be given to trial termination if 2 or fewer patients demonstrate clinical benefit (CR, PR, or SD for at least 3 months). If the trial goes on to the second stage, a total of **35 evaluable**

NU Study Number: NU 16G03

Merck Study Number: 3475-244

patients will be studied. If the total number responding is less than or equal to 6, the combination is rejected.

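### The accrual cap of 46 leaves room for 11 non-evaluable patients, but the Amendment 9 entry that set it already counts 12, so if all enrolled patients count, at most 34 of the planned 35 evaluable patients can be reached

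*Combined protocol and SAP*

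**What the plan says.** The cap and the target appear in four places. The Sample Size row of the Study Summary gives "Maximum accrual limit: 46 Evaluable subjects: 35". The Statistical Methodology row adds "Subjects who are not evaluable for response will be replaced so that up to 46 subjects will be enrolled". Section 3.0 has "A total of up to 46 subjects will be needed to obtain 35 evaluable subjects for this trial", and Section 10.2 has "Subjects who are not evaluable for response will be replaced so up to 46 subjects may be enrolled".

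Under Section 6.2, a patient who has completed at least two cycles "of treatment will be evaluable for this endpoint"; this is the requirement for the primary endpoint. Section 4.11 deals separately with patients who leave before dosing: "If a patient is enrolled in the study but comes off study prior to the first dose of treatment, the patient may be replaced". It does not say whether such a patient uses up one of the 46 places.

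Section 10.4.2 sets the decision rules. At 18 evaluable patients, "consideration will be given to trial termination if 2 or fewer patients demonstrate clinical benefit (CR, PR, or SD for at least 3 months". After stage 2, with 35 evaluable patients, "If the total number responding is less than or equal to 6, the combination is rejected". No rule is given for a final number below 35.

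Appendix V, Amendment 9 (January 2019), explains the figure of 46. The cap had been 38, with 1–3 non-evaluable patients expected. By then 5 patients had enrolled without starting treatment and 7 had received a single cycle, 12 in all. The data and safety monitoring committee had initially agreed to 8 more patients. The entry hopes for 35 evaluable patients with 13–14 drop-outs.

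**The concern.** A cap of 46 and a target of 35 fit together only if no more than 11 patients are lost to the primary endpoint. The entry that justifies the cap reports 12 already lost and forecasts one or two more. On its face, the cap cannot deliver the sample size for which it was set.

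Two things are at stake. The error rates in Section 10.2 (0.047 and 0.098) are calculated for 35 evaluable patients. The final rule is also written for 35, so if accrual closed at 32–34 the primary decision would have no written rule for that number. Choosing one after the responses are known would invite criticism.

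**Working it through.** **Accrual.** Inputs: cap 46 and target 35 (Summary, 3.0, 10.2); two-cycle requirement (6.2); previous cap 38, increase 8, losses 5 and 7, forecast 13–14 (Appendix V, Amendment 9).

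- The cap reproduces: 38 + 8 = 46.
- Losses allowed: 46 − 35 = 11. Losses counted: 5 + 7 = 12. None of the 12 completed two cycles, so none is evaluable.
- The build-up shows the same gap. A cap of 38 allowed 38 − 35 = 3 losses. Twelve losses needed 12 − 3 = 9 more places, a cap of 47, and 8 were added.
- All enrolled count: 46 − 12 = 34 evaluable at most; on the forecast, 46 − 13 = 33 or 46 − 14 = 32.
- Never-dosed do not count: 46 − 7 = 39, so 35 is reachable. Total enrolment is then 35 + 12 = 47, or 35 + 13 = 48 and 35 + 14 = 49 on the forecast.

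**Error rates.** Inputs: null response rate 0.10, alternative 0.30, stage 1 of 18 with cut-off 2, final cut-off 6 (10.2, 10.4.2). For N evaluable patients and true response rate p:

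P(success) = Σₓ P(X₁ = x) · P(stage 2 opens | x) · P(X₂ ≥ 7 − x),

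where X₁ ~ Bin(18, p) and X₂ ~ Bin(N − 18, p). Type I error is this probability at p = 0.10; power is its value at p = 0.30.

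The plan's figures reproduce at N = 35 when stage 2 opens only with 3 or more objective responders: type I error 0.0474 (stated 0.047), type II error 0.0984 (stated 0.098), expected size 22.53 (stated 22.5). The stated rates therefore assume a binding stage 1 gate on objective response.

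The written gate is different. It counts stable disease of at least 3 months as well as response, and it asks only that stopping be considered. Both features make stage 2 easier to open. The other extreme is no stage 1 stop at all. With the final cut-off at 6:

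| N | Binding gate on objective response: type I / power | No stage 1 stop: type I / power |
|---|---|---|
| 35 | 0.047 / 0.902 | 0.055 / 0.935 |
| 34 | 0.042 / 0.892 | 0.048 / 0.922 |
| 33 | 0.037 / 0.880 | 0.042 / 0.906 |
| 32 | 0.033 / 0.865 | 0.036 / 0.887 |

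A binding clinical-benefit gate lies between the two columns. The documents give no rate of stable disease for 3 months, so a range is assumed, with the same rate under both hypotheses:

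| Assumed rate | N = 34: type I / power | N = 35: type I |
|---|---|---|
| 0% | 0.042 / 0.892 | 0.047 |
| 2% | 0.044 / 0.901 | – |
| 3% | – | 0.0502 |
| 10% | 0.047 / 0.918 | 0.054 |
| 30% | 0.048 / 0.922 | 0.055 |

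Like for like, going from 35 to 34 costs 0.9016 − 0.8917 = 0.0099 of power with the binding response gate and 0.9350 − 0.9215 = 0.0135 with no stop. Going to 32 costs 0.9016 − 0.8650 = 0.0366 and 0.9350 − 0.8869 = 0.0481.

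**The case against.** The strongest reply is that the sections in force agree with one another: 46 at most, 35 evaluable. The 12 and the 13–14 appear only in an amendment history entry of January 2019, while the current version dates from November 2020. The entry speaks of a hope and of an initial committee approval that cannot be seen here, and current accrual is not given. This limits how much weight the 13–14 can bear, since it is a forecast. It does not remove the conflict, because the entry is not superseded text on this point: it is the stated basis for the 46 that still stands.

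A second reply is that never-dosed patients may fall outside the cap, since Section 4.11 provides for them separately. The wording leans the other way. Section 4.11 calls such a patient enrolled, Section 10.2 caps the number enrolled, and the Amendment 9 entry includes the 5 never-dosed patients among the losses that justified the increase. Still, no section settles it. A reader might infer a definite shortfall of one patient; the documents support it only on condition that all enrolled patients count.

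A third reply concerns the consequence. A reader might infer that 34 patients miss the type II target, since the binding response gate gives 1 − 0.892 = 0.108. Under the written clinical-benefit gate this fails once about 2% of patients have stable disease for 3 months: 34 patients then meet both targets. This reply stands, and it removes most of the statistical weight of a one-patient shortfall.

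**Conclusion.** The stated size is not delivered by the plan's own loss count if all enrolled patients count towards 46. The maximum is then 34 evaluable patients, reached only if nobody further is lost, and 33 or 32 on the forecast. A reader might take 34 as the expected yield, but it is a ceiling. If never-dosed patients do not count, 35 can be reached, but enrolment of 47 or more contradicts the stated maximum. The text needs reconciling on either reading.

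The effect is small and arises only if stage 2 opens. With the cut-off of 6 kept, type I error stays below 0.050 at 32–34 under every stage 1 reading. At 34 the 0.100 type II target is not clearly missed. At 33 it depends on the stage 1 reading (power 0.880 to 0.906). At 32 it is missed throughout (0.865 to 0.887).

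Nor can one infer that reaching 35 secures the stated 0.047 and 0.098. With the clinical-benefit gate, type I error at 35 passes 0.050 at a stable-disease rate of about 3%, and it rises to as much as 0.055 under that gate or with no stop.

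**What to change.** In the Study Summary and Sections 3.0, 10.2 and 10.4.2, state who counts towards 46 and make the figures follow.

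- **If all enrolled patients count:** say that 46 yields at most 34 evaluable patients (33 or 32 on the forecast losses) and that 6 or fewer responders still means rejection at 32–34. Give type I error and power as ranges: N = 34, 0.042–0.048 and 0.892–0.922; N = 33, 0.037–0.042 and 0.880–0.906; N = 32, 0.033–0.036 and 0.865–0.887. Name the stage 1 rule behind each end: a binding gate on objective response at the lower end, no stage 1 stop at the upper.
- **If never-dosed patients do not count:** say so, and restate the maximum total enrolment as 47 on the counted losses, or 48–49 on the forecast. Do not carry 0.047 and 0.098 over unchanged. State that they assume a binding stage 1 gate on objective response, and that type I error at 35 can reach 0.055 otherwise.

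The cost is wording, through the amendment route in Section 11.2. The first option adds no patients and makes the stated evaluable number slightly less favourable. The second acknowledges 1 enrolment above 46 on the counted losses, or 2–3 on the forecast.

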3.1 Inclusion Criteria

3.1.1 Patients must have a histological or cytological evidence/confirmation of epithelial ovarian cancer, primary peritoneal carcinomatosis, or fallopian tube cancer

3.1.2 Patients must have Measurable disease according to RECIST 1.1 \leq 28 days prior to registration. (Appendix 3).

3.1.3 Patients must have recurrent platinum-resistant disease, defined as progression $<$ 6 months after completion of platinum-based chemotherapy or as persistent disease that remains after completing the most recent line of platinum-based therapy. The platinum-free interval should be calculated from the last administered dose of platinum therapy.

3.1.4 Prior therapy allowed:
•At least one and no more than 3 platinum based chemotherapy regimens.

NU Study Number: NU 16G03
Merck Study Number: 3475-244

- Up to 2 non-platinum, cytotoxic regimens.
- There is no limit on use of prior biological therapies (hormonal or targeted therapy).

NOTE: Prior immunotherapy is not allowed.

3.1.5 Patients must be age ≥ 18 years.

3.1.6 Patients must exhibit an ECOG performance status of 0-1 ≤ 14 days prior to registration (Appendix 2).

3.1.7 Patients must demonstrate adequate organ function as defined in Table 1 below; all screening labs to be obtained ≤ 14 days prior to registration.
(Note: Screening labs will be repeated again on C1D1 if they were performed outside of the ≤ 4 day window.)

Table 1 Adequate Organ Function Laboratory Values

System	Laboratory Value
Hematological	
Absolute neutrophil count (ANC)	$\geq 1,500 / \text{mcL}$
Platelets	$\geq 100,000 / \text{mcL}$
Hemoglobin	$\geq 9 \text{ g/dL}$ or $\geq 5.6 \text{ mmol/L}$ (without transfusion or growth factor support/EPO dependency)
Renal	
Serum creatinine OR Measured or calculated ^a creatinine clearance (GFR can also be used in place of creatinine or CrCl)	$\leq 1.5 \times \text{upper limit of normal (ULN)}$ OR $\geq 60 \text{ mL/min}$ for subject with creatinine levels $> 1.5 \times$ institutional ULN.
Hepatic	
Serum total bilirubin	$\leq 1.5 \times \text{ULN}$ OR Direct bilirubin $\leq \text{ULN}$ for subjects with total bilirubin levels $> 1.5 \text{ ULN}$
AST (SGOT) and ALT (SGPT)	$\leq 2.5 \times \text{ULN}$ OR $\leq 5 \times \text{ULN}$ for subjects with liver metastases.
Albumin	$\geq 2.5 \text{ mg/dL}$
Coagulation	
International Normalized Ratio (INR) or Prothrombin Time (PT)	$\leq 1.5 \times \text{ULN}$ unless subject is receiving anticoagulant therapy as long as PT or PTT is within therapeutic range of intended use of anticoagulants.
Activated Partial Thromboplastin Time (aPTT)	$\leq 1.5 \times \text{ULN}$ unless subject is receiving anticoagulant therapy as long as PT or PTT is within therapeutic range of intended use of anticoagulants.

^aCreatinine clearance should be calculated per institutional standard.

3.1.8 Be willing to allow the use of archival formalin-fixed paraffin-embedded tumor tissue for correlative analyses.

Note: The archived tumor tissue specimens may be from prior surgery or from prior diagnostic biopsy of primary or metastatic tumor specimen.

Unavailability of archived tissue will not render subject ineligible for study.

3.1.9 Be willing and able to undergo a core or excisional tumor biopsy according to institutional standards (guided visually or by computed tomography [CT] or ultrasound), paracentesis, or thoracentesis for tumor cells.

Note: This is to be done prior to treatment at C1D1 and post-treatment (Cycle 2 Day 8), if this is clinically and safely feasible to do so. This will allow the use of this freshly obtained tissue for correlative analyses in the study.

NU Study Number: NU 16G03
Merck Study Number: 3475-244

3.1.10 Females of child-bearing potential (FOCBP) must agree to use adequate contraception (Appendix 1) prior to registration, for the duration of study participation, and for 120 days following completion of therapy. Should a female patient become pregnant or suspect she is pregnant while participating in this study, she should inform her treating physician immediately.

NOTE: A FOCBP is *any woman* (regardless of sexual orientation, having undergone a tubal ligation, or remaining celibate by choice) who meets the following criteria:

- *Has not* undergone a hysterectomy or bilateral oophorectomy
- *Has had* menses at any time in the preceding 12 consecutive months (and therefore has not been naturally postmenopausal for > 12 months)

3.1.11 FOCBP must have a negative pregnancy test ≤ 7 days prior to registration on study.

3.1.12 Patients must have the ability to understand and the willingness to sign a written informed consent prior to registration on study.

3.2 Exclusion Criteria

3.2.1 Has had prior chemotherapy, targeted small molecule therapy, or radiation therapy ≤ 14 days prior to registration or who has not recovered (i.e., \leq Grade 1 or at baseline) from adverse events due to a previously administered agent.

NOTE: *Subjects with \leq Grade 2 neuropathy are an exception to this criterion and may qualify for the study.*

NOTE: *If subject received major surgery, they must have recovered adequately from the toxicity and/or complications from the intervention prior to starting therapy.*

3.2.2 Has had a prior anti-cancer monoclonal antibody (mAb) ≤ 28 days prior to registration or who has not recovered (i.e., \leq Grade 1 or at baseline) from adverse events due to agents administered more than 4 weeks earlier.

3.2.3 Is currently participating and receiving study therapy or has participated in a study of an investigational agent and received study therapy or used an investigational device ≤ 28 days prior to registration.

3.2.4 Has a diagnosis of immunodeficiency or is receiving systemic steroid therapy or any other form of immunosuppressive therapy ≤ 7 days prior to the first dose of trial treatment.

3.2.5 Has a known additional malignancy that is progressing or requires active treatment. Exceptions include basal cell carcinoma of the skin or squamous cell carcinoma of the skin that has undergone potentially curative therapy or *in situ* cervical cancer.

3.2.6 Has known active central nervous system (CNS) metastases and/or carcinomatous meningitis. Subjects with previously treated brain metastases may participate provided they are stable (without evidence of progression by imaging for at least 28 days prior to registration and any neurologic symptoms have returned to baseline), have no evidence of new or enlarging

NU Study Number: NU 16G03
Merck Study Number: 3475-244

brain metastases, and are not using steroids for at least 7 days prior to trial treatment. This exception does not include carcinomatous meningitis which is excluded regardless of clinical stability.

- 3.2.7** Has active autoimmune disease that has required systemic treatment in the past 2 years (i.e. with use of disease modifying agents, corticosteroids or immunosuppressive drugs). Replacement therapy (e.g. thyroxine, insulin, or physiologic corticosteroid replacement therapy for adrenal or pituitary insufficiency, etc.) is not considered a form of systemic treatment.
- 3.2.8** Has received prior therapy with an anti-PD-1, anti-PD-L1, or anti-PD-L2 agent. *Please contact the Principal Investigator for further clarification if needed.*
- 3.2.9** Hypersensitivity to pembrolizumab or any of its excipients.
- 3.2.10** Has a known history of active TB (Bacillus Tuberculosis).
- 3.2.11** Has a known history of Human Immunodeficiency Virus (HIV) (HIV 1/2 antibodies) infection.
- 3.2.12** Has a known history of Hepatitis B and/or Hepatitis C infection.
- 3.2.13** Has known history of (non-infectious) pneumonitis that required steroids, or current pneumonitis.
- 3.2.14** Has an active infection requiring systemic therapy within 3 days of registration (NOTE: except for uncomplicated Urinary Tract Infection (UTI)).
- 3.2.15** Has a history or current evidence of any condition, therapy, or laboratory abnormality that might confound the results of the trial, interfere with the subject's participation for the full duration of the trial, or is not in the best interest of the subject to participate, in the opinion of the treating investigator.
- 3.2.16** Has known psychiatric or substance abuse disorders that would interfere with cooperation with the requirements of the trial.
- 3.2.17** Has received a live vaccine ≤30 days of planned start of study therapy.
Note: Seasonal influenza vaccines for injection are generally inactivated flu vaccines and are allowed; however intranasal influenza vaccines (e.g., Flu-Mist®) are live attenuated vaccines, and are not allowed.
- 3.2.18** Female patients who are pregnant or nursing, or expecting to conceive within the projected duration of the trial, starting with the pre-screening or screening visit through 120 days after the last dose of trial treatment. *Subjects should not breast feed ≤120 days of completing the trial.*
- 3.2.19** Is or has an immediate family member (e.g., spouse, parent/legal guardian, sibling or child) who is investigational site or sponsor staff directly involved with this trial, unless prospective IRB approval (by chair or designee) is given allowing exception to this criterion for a specific subject.

